## 8.5 Laboratory Procedures

All laboratory assessments will be performed locally at each center's laboratory by means of their established methods (using site specific laboratory normal values). Blood samples should be taken using standard venipuncture techniques according to the laboratory guidelines. The approximate total blood volume that will be taken for the laboratory and biomarker assessments will be 50 to 60 mL.

## 8.6 STUDY VISIT REQUIREMENTS

The Schedule of Procedures is outlined in Appendix A.

### 8.6.1 Day -2 to Day -1: Screening

Within 48 hours prior to scheduled excision and STSG surgery, subjects will undergo the following screening assessments:

- Written informed consent from the patient or their legally authorized representative

- Age, gender, height and weight
- Inclusion and exclusion criteria evaluation
- Medical history
- Concomitant medications
- Physical examination
- Vital signs
- Biomarkers
- Laboratory tests
  - CBC with platelets
  - INR, PTT
  - Electrolytes, alkaline phosphatase, AST, ALT, bilirubin, total protein, albumin, BUN, creatinine, and, for patients with diabetes only, evaluation of HbA1c levels
  - Blood draw (4-5mL) to obtain serum for subsequent testing for burn biomarkers
- Pregnancy test for female subjects
- Evaluation of suitability and probable body location for fat harvest by the surgical specialist who will perform the lipoaspirate procedure

Enrollment will occur by a designated staff following confirmation by the treating surgeon that the patient is to proceed with a skin graft from the patient's donor site. Enrollment will occur within 2 hours of the scheduled procedure.

## 8.7 Procedure Day (Day 1)

The following assessments are to be conducted:

- For All Subjects
  - Randomization
  - Vital signs
  - Assessment for adverse events
  - Digital photography of wounds
  - Laboratory tests
    - CBC with platelets
    - INR, PTT
    - Electrolytes, alkaline phosphatase, AST, ALT, bilirubin, total protein, albumin, BUN, creatinine
- For Subjects Randomized to Treatment Arm only
  - Low volume fat harvest
  - Microbiology testing of dose samples (ADRCs) at baseline (prior to ADRCs administration)
  - ADRC dose preparation and delivery

### 8.7.1 Fat Harvest

#### 8.7.1.1 General Requirements

- Fat harvest will be performed at the start of general anesthesia for the planned excision and STSG

- In order to ensure that surgical resources for standard of care escharectomy are not diverted to the fat harvesting procedure, fat harvest will be performed by a qualified surgeon not otherwise involved in the burn surgery at that time.
- Standard tissue calipers or expert surgical specialist examination should be used to assess possible body sites for subcutaneous fat tissue. Any subject with an active skin infection at the site of lipoharvest will be excluded from the study
- Fat harvest should NOT be performed if an anticoagulant has been administered within 1 hour prior, a substantial anticoagulant such as a Glycoprotein IIb/IIIa inhibitor/anti-platelet class drug was administered within 2 weeks prior (such as ReoPro, Integrilin or Aggrastat), or if there is an abnormally high INR or PTT

Operative details such as start and stop time, weight of lipoaspirate, dose preparation time will be recorded on the appropriate eCRF.

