### 4.7 Inclusion and Exclusion Criteria

#### 4.7.1 *Inclusion Criteria*

Subjects will be enrolled into this study only if they meet ALL of the following criteria:

1. Males or females,  $\geq 18$  to  $\leq 65$  years of age
2. BMI  $> 20$  kg/m^2
3. Burn TBSA 20% - 50%
4. At least one deep partial thickness and/or full thickness thermal burn  $\geq 250$  cm^2 on the arms, legs, back, abdomen or chest that is anticipated to be covered with a meshed autologous STSG and that has not been treated previously with a biologic dressing such as Alloderm® or Integra®
5. Ability to safely undergo adipose tissue harvest procedure that is anticipated to yield  $\geq 150$  mL of adipose tissue at a site that is free from infection
6. Donor site availability for skin graft harvest

7. Able to provide written informed consent, signed by either the patient or their legally authorized representative
8. Women and men of child-bearing potential agreeing to use contraception during the study. Acceptable methods include surgical sterility, IUDs, hormonal contraception or double barrier methods.

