## 5.2 Randomization and Subject Identification

Randomization to ADRC and usual care will occur within 2 hours prior to the scheduled surgery for STSG.

Randomization will be done via an interactive web response system (IWRS). Subjects will be randomized in a 2:1 ratio to receive intravenous delivery of either Celution® System processed ADRCs with usual care or to usual care alone.

A total of up to 15 subjects will be enrolled. Each patient will contribute up to three qualified wound areas for the analysis. If more than one wound is identified, each must be noncontiguous with the other(s). Therefore, between 15 and 45 wounds will be evaluated.

The 1st 5 subjects enrolled in active treatment will be observed for adverse events over a 7 day period. If no SAEs occur during that period, for that individual subject, the next subject enrolled in active treatment may be entered with the same 7 day observation period. The safety results of the first 5 subjects will be reviewed by the DMC and their evaluation will be used in conjunction with the clinical data collected to date, and if appropriate, to potentially remove the staggering approach to the study. Enrollment after the first 5 subjects enrolled in active treatment may continue only after the DMC has completed its safety review and recommends continuation.

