### **7.1.1 Treatment Dose Control**

ADRC count and viability will be determined using a validated system that counts both viable and non-viable nucleated cells (NC-100 NucleoCounter® Automated Cell Counting System, Enfield, Connecticut, USA) using the following criteria:

- Nominal cell count:  $20 \times 10^6$  ADRCs
- A minimum cell count within 15% of the nominal cell count is required (i.e., a dose as low as  $17 \times 10^6$  ADRCs is acceptable if  $20 \times 10^6$  ADRCs is not available)
- Cell viability:  $\geq 70\%$
- If cell viability is  $< 70\%$ , as determined by the NucleoCounter® Automated Cell Counting System, the subject will not be treated but will be followed per study protocol for safety.
- Negative result in Gram stain testing (see *Section 7.2*)
- If the Gram stain testing result is positive, the subject will not be treated but will be followed per study protocol for safety.

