#### **10.5 Withdrawal, ITT, PTE**

Reasons for withdrawal pre- and post-randomization will be summarized. The treatment analyses will be performed on intent-to-treat basis as well as on a per-treatment-evaluable basis, as defined below:

Intent-to-Treat (ITT): All randomized subjects; randomization will occur on procedure day prior to the tissue harvest procedure. Subjects will be included in the analysis according to the treatment assigned if population is different than PTE.

Per-Treatment-Evaluable (PTE): All enrolled subjects who have day 5 follow-up information available.

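### The harvest-site infection exclusion in 8.7.1.1 is not limited to the time before randomization and could take a randomized ADRC subject out of follow-up and out of the feasibility count

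*Protocol*

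**What the plan says.** Section 8.7.1.1 lists general requirements for the fat harvest, under the heading for Procedure Day (Day 1). One bullet first describes how sites are assessed: "Standard tissue calipers or expert surgical specialist examination should be used to assess possible body sites for subcutaneous fat tissue". It then states: "Any subject with an active skin infection at the site of lipoharvest will be excluded from the study". It names no day for this check and no consequence for the analysis.

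An infection-free harvest site is also part of eligibility. Inclusion criterion 5 (4.7.1) asks for an anticipated yield of at least 150 "mL of adipose tissue at a site that is free from infection". Screening (8.6.1) includes this item for every subject: "Evaluation of suitability and probable body location for fat harvest by the surgical specialist who will perform the lipoaspirate procedure".

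On timing, 5.2 says: "Randomization to ADRC and usual care will occur within 2 hours prior to the scheduled surgery for STSG". Section 8.7.1.1 says: "Fat harvest will be performed at the start of general anesthesia for the planned excision and STSG". Controls have no harvest (section 7).

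On analysis, 10.5 defines intent-to-treat as "All randomized subjects; randomization will occur on procedure day prior to the tissue harvest procedure". Section 10 makes this the primary analysis population, and 10.6 rules out imputation. For cells with low viability or a positive Gram stain, 7.1.1 says that "the subject will not be treated but will be followed per study protocol for safety".

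**The concern.** An eligibility exclusion stands in a section that describes a step taken after randomization and in one arm only, and nothing limits it to the time before randomization. If an infection is first noticed when the surgeon comes to harvest, the literal instruction is to exclude a subject who is already randomized to ADRC. A control whose unused site became infected over the same interval would not be looked at again and would stay in.

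Two things are at stake. The first is the comparison between arms: a removal that can happen in only one arm weakens what randomization provides. The second is feasibility, which is part of the primary endpoint and includes the ability to perform the harvest (10.3.1). A subject who could not be harvested is a feasibility failure, and removing that subject would hide the failure.

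**Working it through.** The protocol states no figure on this point, so the check sets its sections side by side.

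**1. Order of events.**
- Day -2 to Day -1, within 48 hours before surgery: eligibility check and harvest-site evaluation, all subjects (8.6.1). Appendix A marks the inclusion and exclusion check in this column only.
- Day 1, within 2 hours before surgery: randomization, all subjects (5.2, 8.7).
- Day 1, start of anesthesia: harvest, ADRC arm only (8.7, 8.7.1.1).

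**2. Does screening close the gap?** Not fully. The screening evaluation yields only a probable location. Section 8.7.1.2 prefers the abdomen but has several sites evaluated and prepared, with other regions as a fallback. The site actually used may therefore be settled on Day 1, and no eligibility check is scheduled for that day. An infection first seen then meets only the 8.7.1.1 sentence.

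**3. How are other randomized ADRC subjects handled when a step cannot be completed?**

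| Situation | Section | Consequence stated |
|---|---|---|
| Low viability or positive Gram stain | 7.1.1, 7.2 | No treatment; followed for safety |
| Liposuction done, cells fail release | 10.3 | Kept in feasibility and in intent-to-treat; safety analyzed separately; out of the per-treatment-evaluable (PTE) set for efficacy |
| Recent anticoagulant, or abnormally high INR or PTT | 8.7.1.1, next bullet | Harvest withheld; no exclusion from the study stated |
| Infection at the harvest site | 8.7.1.1 | Excluded from the study |

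Only the last row takes the subject out of the study.

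**4. Does any other section keep this subject in?**
- Section 10.5 keeps the subject in intent-to-treat by definition. Without follow-up and without imputation (10.6), however, the subject would contribute no later outcomes.
- Section 10.3 does not help, because its protection begins only once liposuction has been done.
- Section 5.1 item 4 makes enrollment in the ADRC arm depend on the start of harvest. This subject would be randomized but not enrolled, so would not count toward the 15 enrolled subjects (4.3) and would fall outside PTE, which is limited to enrolled subjects (10.5). A control needs no harvest to be enrolled.

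**5. Scale, for illustration only.** At full enrollment and 2:1:
- ADRC: 15 × 2/3 = 10. Control: 15 × 1/3 = 5.
- One removal: 1/10 = 10% of the ADRC arm, 0/5 = 0% of controls.
- If the other nine succeed, feasibility is 9/10 = 90% with the subject counted and 9/9 = 100% with the subject dropped.

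How often this would occur is not given.

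**The case against.** The strongest reply is that the sentence only restates inclusion criterion 5. It follows a remark on assessing possible body sites, which is what screening schedules for everyone, and exclusion from the study is the language of eligibility. That reading is reasonable and may be the intended one. It does not say what to do when the infection appears after randomization, and the placement invites the other reading.

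Several stronger readings are tempting, and the document does not support them.
- A reader might infer that the protocol prescribes a Day 1 infection check in the ADRC arm only. It does not; that timing comes from where the sentence stands.
- A reader might infer a stated contradiction of intent-to-treat. The definition in 10.5 is unconditional, and 8.7.1.1 removes nobody from an analysis set. Section 10.5 also summarizes withdrawals after randomization, and 8.11 provides an early termination visit. The conflict is one of effect: no follow-up and no imputation.
- A reader might take 9/9 as the planned result. Section 10 with 10.3.1 can equally be read to give 9/10. The risk comes from 5.1 and from the gap in 10.3.
- A reader might infer that the removed subjects would have had poorer graft take. The document says nothing on that, and the infection concerns the harvest site, not the graft.

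It is also fair that 7.1.1 covers subjects already harvested, so its different wording is not in itself an inconsistency. The trigger is narrow too: screening is at most 48 hours earlier, and another site may be usable. These points limit the size of the problem but leave the case unregulated.

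**Conclusion.** The point holds as a gap with a conflict in effect. Section 8.7.1.1 does not confine its exclusion to the time before randomization. For an infection first found on Day 1, its literal wording would take a randomized ADRC subject out of follow-up, 10.3 would not protect that subject, and 5.1 would not count the subject as enrolled. A harvest failure could then disappear from a primary feasibility measure.

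This rests on two assumptions: that an infection can first be noticed between screening and harvest, and that site staff would apply the sentence as written. The likely number of cases is unknown. With about 10 ADRC subjects, a single case would be 10% of the arm. The study is not powered for hypotheses (10.2), so the issue is an accurate account of feasibility and of the randomized groups, not a test result. A correction is worth making because it is cheap and removes an avoidable one-arm loss.

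**What to change.** 1. In 8.7 and Appendix A, add a Day 1 confirmation of inclusion criterion 5 for all subjects, before the IWRS randomization.
2. In 8.7.1.1, state that exclusion from the study for infection at the harvest site applies only before randomization.
3. In the same place, and in 10.3, state that a randomized ADRC subject in whom harvest is not started stays in scheduled follow-up, is analyzed in the ADRC arm under intent-to-treat, and counts as a harvest failure for feasibility.
4. Reconcile 5.1 item 4 with this, so that being counted in the ADRC arm does not depend on an event after randomization.

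The clinical decision whether to harvest is left as it is. The cost is a few sentences and one mark in Appendix A, with no new visit or laboratory test. The reported feasibility rate may be slightly less favorable.

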#### **8.7.1.2 Fat Harvest Procedure:**

A specific set of requirements has been established for the collection of fat that can then be used for the successful preparation of ADRCs using the Celution® technology. Therefore, the following conditions and procedures are to be used. Additional information will be provided in the Celution® Instructions for Use:

- Syringe-based fat harvest is required
- A total volume of 100-150 mL of adipose tissue must be harvested
- Symmetric fat removal is required, keeping the overall area of aspiration as small as possible
- The abdominal region is the preferred site for fat harvest, however multiple sites should be evaluated and prepared and non-abdomen regions (e.g., inner thigh) used if abdomen not available
- Make an approximately 0.5 cm stab skin incision
- Infiltrate tumescent solution using a 14 gauge, up to 30 cm, blunt LAMIS™ infiltrator for tumescent fluid administration ; tumescent fluid should be infiltrated at a ratio of approximately 1:1 to 3:1 of tumescent solution to fat to be harvested
- The tumescent fluid formula to be used is:
  - 500 mL of Lactated Ringers solution
  - 20-50 mL of 1% Lidocaine
  - 1 mg of epinephrine
- To sufficiently induce vasoconstriction/hemostasis during the tissue harvest procedure a minimum of 100 mL of tumescent fluid must be used. Estimated volume should generally be limited to 500 mL
- Approximately 10 minutes after the tumescent fluid injection, the adipose tissue is harvested through the same incision, using an up to 32 cm long, 3-5 mm inner diameter Toomey cannula with a Mercedes standard tip attached to a sterile 60 mL Toomey syringe
- After the first syringe is filled (complete filling is not required) it is detached from the cannula, capped with a sterile cap and set aside; additional syringes are filled until the desired amount of fat is harvested
- Fat harvest will be limited to areas where tumescent fluid has been infiltrated
- Vital signs are monitored during tissue harvest procedure
- Close surgical incision as per the surgeon's standard procedure. Apply pressure bandage immediately upon conclusion of tissue harvest

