## 6 CELUTION® SYSTEM

### 6.1 Celution® System Description

The Celution® System consists of a stand-alone re-useable hardware unit called the Celution® 800/IV Device with v5.1 firmware with Heater Attachment accessory, the Celution® 805/IV Consumable Set, Celase® and Intravase®. The Celution® System prepares an ADRC output from adipose tissue collected by standard syringe aspiration techniques. The tumescent fluid is composed of: 500 mL of lactated Ringers solution, 20 mL of 1% lidocaine, and 1mg of epinephrine.

Following the collection and preparation of tissue via fat harvest, the adipose tissue is introduced into the device's collection canister in order to wash the adipose tissue and remove deleterious substances (such as cellular debris) (Detailed instructions for use are found in the *Celution® User Manual*).

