### **9.6.1 Fat Harvest Risk Management**

The Investigators and all study personnel will be trained in the details of all aspects of the study procedures. Standardization of fat harvest techniques is critical to a good clinical outcome. To minimize risks and increase the chances of a favorable clinical outcome the following measures are required for the liposuction procedure:

- Performed by an appropriately licensed and credentialed physician
- Monitoring of vital signs throughout the procedure
- Sterile technique is followed throughout
- The adipose tissue is handled gently at all times
- HGB, HCT prior to and 1-2 hours post-procedure

- To sufficiently induce local vasoconstriction/hemostasis during the fat harvest procedure, a minimum of 500 mL and a recommended maximum of 2000 mL of tumescent fluid is used containing:
  - 500 mL of Lactated Ringers solution
  - 20-50 mL of 1% Lidocaine
  - 1 mg of epinephrine
- A blunt 14 to 16 gauge LAMIS infiltrator (or equivalent) will be used for infiltration with tumescent solution
- After approximately 10 minutes, the adipose tissue may be harvested through the same incision, using the aspiration cannula attached to a syringe
- A blunt cannula with a minimum inner diameter of 3 mm is preferred for lipoaspiration.
- Lipoaspiration is done manually using a syringe (60 mL Toomey syringe is preferred); no machine aspiration is permitted.
- Monitoring for prevention or early detection of bleeding:
- Enrollment of only patients who qualify per the inclusion / exclusion criteria defined in the protocol) including screening blood work
- Strict adherence to the study protocol
- Standard of care for the monitoring and treatment of subjects who experience any adverse event for liposuction
- Target volume of adipose tissue is limited to approximately 100-150 mL
- Close surgical incision with appropriate suture
- Apply pressure bandage immediately upon conclusion of tissue harvest

Fat harvest should NOT be performed on patients who have received any anticoagulant within 1 hour of the procedure, substantial anticoagulation (eg: GIIb/IIIa inhibitor class drugs) within two weeks prior to fat harvest, or who have an abnormal PTT.

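### Protocol 9.6.1 requires at least 500 mL of tumescent fluid for a harvest for which 8.7.1.2 implies about 100-450 mL

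*Protocol*

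**What the plan says.** Two sections of the Protocol instruct the surgeon on tumescent infiltration.

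- **8.7.1.2 (Fat Harvest Procedure).** The harvest is fixed: "A total volume of 100-150 mL of adipose tissue must be harvested". On the ratio: "tumescent fluid should be infiltrated at a ratio of approximately 1:1 to 3:1 of tumescent solution to fat to be harvested". On the volume: "a minimum of 100 mL of tumescent fluid must be used. Estimated volume should generally be limited to 500 mL". The formula is 500 mL lactated Ringers, 20-50 mL of 1% lidocaine and 1 mg epinephrine.
- **9.6.1 (Fat Harvest Risk Management).** The list is introduced with the statement that "the following measures are required for the liposuction procedure". One item is "a minimum of 500 mL and a recommended maximum of 2000 mL of tumescent fluid is used containing" the same three ingredients in the same amounts as in 8.7.1.2. Another item on the list reads: "Target volume of adipose tissue is limited to approximately 100-150 mL".

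Both sections give the same reason for the fluid, vasoconstriction and hemostasis at the harvest site.

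Two smaller points concern the same procedure. Section 6.1 gives a single lidocaine amount: "The tumescent fluid is composed of: 500 mL of lactated Ringers solution, 20 mL of 1% lidocaine, and 1mg of epinephrine". Section 9.6.1 also requires "HGB, HCT prior to and 1-2 hours post-procedure", whereas the Day 1 CBC in 8.7 and Appendix A has no stated time.

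**The concern.** The purpose, formula and harvest volume are the same in both sections, so 9.6.1 cannot be read as describing a different or larger liposuction. The two minimums differ fivefold (100 mL and 500 mL), and the upper limit in 9.6.1 is four times the usual one in 8.7.1.2. A surgeon who infiltrates less than 500 mL, as the 8.7.1.2 ratio directs, misses a measure that 9.6.1 calls required. A surgeon who works from 9.6.1 may give volumes, with the lidocaine and epinephrine they contain, that 8.7.1.2 does not intend for so small a harvest.

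This matters because adverse events related to the lipoharvest are part of the primary endpoint (4.6.1), and section 9.10 acknowledges that the safety of liposuction in burn patients has not been established. With so few treated subjects, the harvest exposure should be the same by design. Deviations are also to be graded minor or major (10.7), which needs one volume standard to grade against.

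**Working it through.** **Inputs.** Fat volume 100-150 mL (8.7.1.2 and 9.6.1); ratio about 1:1 to 3:1, minimum 100 mL, general limit 500 mL (8.7.1.2); minimum 500 mL, recommended maximum 2000 mL (9.6.1); lidocaine per bag 20 mL (6.1) or 20-50 mL (8.7.1.2, 9.6.1); up to 15 subjects at 2:1 (4.1, 4.3).

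**Step 1. Is 8.7.1.2 consistent with itself?** Volume = ratio × fat volume.

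- 100 mL of fat: 1 × 100 = 100 mL to 3 × 100 = 300 mL
- 150 mL of fat: 1 × 150 = 150 mL to 3 × 150 = 450 mL

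The lowest value equals the stated 100 mL minimum and the highest lies under the 500 mL limit. The section is consistent.

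**Step 2. What ratios does 9.6.1 imply?** Ratio = fluid volume / fat volume.

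| Fluid | 150 mL of fat | 100 mL of fat |
|---|---|---|
| 500 mL (minimum) | 500/150 = 3.3:1 | 500/100 = 5:1 |
| 2000 mL (recommended maximum) | 2000/150 = 13.3:1 | 2000/100 = 20:1 |

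**Step 3. Where do the sections meet?** The volume ranges are 100-500 mL and 500-2000 mL, so they share only 500 mL. That exceeds 3:1 at every permitted harvest volume. No volume meets the 9.6.1 minimum and stays strictly within 3:1.

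- Shortfall of the top of the 8.7.1.2 ratio against the 9.6.1 minimum: 500 − 450 = 50 mL (150 mL of fat); 500 − 300 = 200 mL (100 mL of fat)
- Upper limits: 2000/500 = 4

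**Step 4. Drug content.** One bag is 500 + 20 = 520 mL with 20 mL × 10 mg/mL = 200 mg lidocaine, or 500 + 50 = 550 mL with 50 mL × 10 mg/mL = 500 mg. Each bag holds 1 mg epinephrine, whose own volume is neglected. Larger volumes are assumed to use further bags of the same formula.

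| Infiltrated | Lidocaine, 20 mL per bag | Lidocaine, 50 mL per bag | Epinephrine |
|---|---|---|---|
| 500 mL | 500 × 200/520 = 192 mg | 500 × 500/550 = 455 mg | 500/520 = 0.96 mg; 500/550 = 0.91 mg |
| 2000 mL | 2000 × 200/520 = 769 mg | 2000 × 500/550 = 1818 mg | 2000/520 = 3.85 mg; 2000/550 = 3.64 mg |

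**Step 5. Subjects affected.** 15 × 2/3 = 10 at full enrolment.

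**The case against.** The strongest reply is that the wording of 8.7.1.2 is soft. Its only firm fluid limit is the 100 mL floor; the ratio is approximate and the 500 mL ceiling holds only in general. The 2000 mL in 9.6.1 is likewise only recommended. A surgeon who gives 500 mL for 150 mL of fat can fairly claim to follow both sections. That stands. The shortfall against 9.6.1 arises only below 500 mL.

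The 100 mL case may also be uncommon. The ratio refers to the fat planned for removal, eligibility asks for an anticipated yield of at least 150 mL (4.7.1), and the feasibility endpoint needs more than 100 mL (4.6.1). This reduces the weight of the 5:1, 20:1 and 200 mL figures. It does not remove the conflict, because 8.7.1.2 permits any harvest from 100 to 150 mL and, at 150 mL, still sanctions infiltrating 150-450 mL, all below the 9.6.1 minimum.

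Surgeons would probably work from 8.7.1.2, and 9.6.1 sits in the risk/benefit chapter. But 9.6.1 calls its measures required, so its place in the document does not make it background.

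The drug masses do not show harm. The Protocol gives no dose threshold, and the figures at 2000 mL assume that someone uses the full recommended maximum. They show only how far apart the permitted exposures lie. Vital-sign monitoring, harvest stopping rules, staggered entry and DMC review all limit the consequences. None of them tells the surgeon which volume is intended.

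The lidocaine amount in 6.1 lies within the 20-50 mL range, and the untimed Day 1 CBC does not contradict the timed check in 9.6.1. Both are minor alignments, and the main point does not depend on them.

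**Conclusion.** The concern holds. Two current sections give incompatible tumescent volumes for one procedure. They can be reconciled only at 500 mL and only near the top of the harvest range, and for 100 mL of fat they cannot be reconciled. The gap is 50-200 mL at the lower end of 9.6.1 and a factor of four at the upper limits, in at most about 10 treated subjects.

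The volume comparison rests on the Protocol's own figures. The drug masses also rest on the bag assumptions stated with them and imply no toxicity finding. This is an inconsistency in a safety instruction. It does not affect sample size or error rates and does not invalidate the trial, but it should be corrected.

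**What to change.** - **9.6.1:** replace the 500 mL minimum and 2000 mL recommended maximum with the 8.7.1.2 limits: minimum 100 mL, generally no more than 500 mL, about 1:1 to 3:1 to the fat. The sponsor's clinical lead should confirm that these are the intended values.
- **6.1:** in the same edit, align the lidocaine amount with the 20-50 mL in 8.7.1.2 and 9.6.1.
- **8.7 and Appendix A (minor):** add the hemoglobin and hematocrit check 1-2 hours after the harvest to the treatment-arm items for Day 1, with a matching footnote to the schedule. The CBC at first dressing change comes too late to replace it.

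The cost is wording in two sections, one line in 8.7 and one footnote. No assessment is added beyond what 9.6.1 already requires, and the sample size is unchanged.
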